# **16.Trial Organisational Structure**

# 16.1. Sponsor

Nottingham University Hospitals NHS Trust will undertake the role of Sponsor as defined by the UK Policy Framework for Health and Social Care Research. Delegated responsibilities will be assigned to the Chief Investigator, participating NHS Trusts and Nottingham Clinical Trials Unit.

Trial	TB-DILI Trial	Protocol	1.2	date:	02-Aug-2022	Page 48 of 58
name:		version:				

## 16.2. Trials Unit

The trial is co-ordinated by the Nottingham Clinical Trials Unit (NCTU).

## 16.3. Trial Management Group

The TMG will be responsible for the day-to-day management of the trial. Membership includes (but is not limited to) the CI, Deputy Chief Investigator, Trial Manager, Trial Statistician and other members of the NCTU multidisciplinary team as appropriate. The TMG will ensure high quality trial conduct, to time and within budget, monitor all aspects of the conduct and progress of the trial, ensure that the protocol is adhered to and take appropriate action to safeguard participants and the quality of the trial itself. The TMG will also be responsible for ensuring project milestones are achieved. The TMG will meet regularly during the entire course of the trial.

## 16.4. Trial Steering Committee (TSC)

A TSC will be established which includes an independent chair, independent and non-independent members and patient representatives. The role of the TSC is to provide oversight of the trial. A meeting will take place 6 months and 18 months after the first participant is recruited with all meetings thereafter taking place approximately every six months during the recruitment phase of the trial.

TSC members will be asked to sign the TB-DILI TSC Charter which will outline their roles and responsibilities. The TSC will consider and act, as appropriate, upon the recommendations of the DMC, and in accordance with the TSC Charter, and ultimately carries the responsibility for deciding whether the trial needs to be stopped on the grounds of safety or efficacy.

The TSC will consider and act, as appropriate, upon the recommendations of the Data Monitoring Committee (DMC).

## 16.5. Data Monitoring Committee

Reports will be supplied in confidence to an independent DMC, which will be asked to give advice on whether the accumulated data from the trial, together with the results from other relevant research, justifies the continuing recruitment of further participants. The DMC will operate in accordance with a trial specific charter based upon the template created by the Damocles Group.

During the recruitment phase of the trial, the DMC is scheduled to meet 6 months and 18 months after the recruitment of the first participant and annually thereafter.

Additional meetings may be called if recruitment is much faster than anticipated and the DMC may, at their discretion, request to meet more frequently or continue to meet following completion of recruitment. An emergency meeting may also be convened if a safety issue is identified. The DMC will report directly to the TSC who will convey the findings of the DMC as appropriate (e.g. MHRA, funder, and/or Sponsor).

At the first DMC meeting, the committee will be presented with the data required to assess the stopgo criteria for the internal pilot phase of the trial (see section 14.2.1). The DMC and TSC will review the data against the stop-go criteria and advise whether the trial should continue, outlining any concerns/modifications required for continuation (if applicable).

Trial	TB-DILI Trial	Protocol	1.2	date:	02-Aug-2022	Page 49 of 58
name:		version:				

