# 1 Background and Rationale

## 1.1. Background

In 2018, 4,655 people were diagnosed with tuberculosis (TB) in the UK, equivalent to a rate of TB of 8.3 per 100,000 population. This was the lowest recorded rate of TB in the UK for the last 10 years. People born outside the UK accounted for 72% of notifications in 2018. The proportion of people with drug-sensitive TB who completed treatment by 12 months was 84.7% in 2017; in addition, 5.3% died and 4.2% were lost to follow up. Only 2.7% of people with TB were coinfected with HIV in 2018; most (81.7%) were born outside the UK. Early data from 2019 suggests that the rate of TB may be higher in 2019 compared to 2018.

The standard treatment of drug-sensitive TB involves a 4-drug combination of anti-TB therapy (ATT) for 2 months (intensive phase of treatment), followed by a 2-drug combination for 4 months (continuation phase of treatment), making a total treatment duration of 6 months. Cure rates are around 97%.9

Drug-induced liver injury (DILI) is the commonest serious adverse effect of ATT. DILI may result from direct toxicity of the primary compound or an immunological response to one or more of the drugs. Unpredictable or idiosyncratic reactions which develop acutely account for most types of DILI. These reactions are unpredictable based on the pharmacological action of the drug, independent of drug dose and are relatively unusual for each drug.

Among those who develop DILI on ATT, 16% develop jaundice and 5.3% acute liver failure; the latter is the most severe outcome of DILI, of which 22% can be fatal. Most patients with DILI who report symptoms experience nausea, vomiting, anorexia and lethargy. Early detection of DILI with cessation of the inciting drug(s) serves to limit the severity of DILI and its consequences. Not all asymptomatic increases in liver enzymes while on ATT constitute DILI episodes. Some of the increase in liver enzymes are self-limiting or are attenuated through a process called hepatic adaptation (please see later). However, very high levels of liver enzymes (>5x upper limit of normal) in the absence of symptoms are thought to represent early DILI episodes that, if left untreated (ie. continued exposure to the inciting drug(s)), would progress to symptomatic DILI.

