# 10.3. Events that do not require reporting

Individuals who develop a DILI significant enough to require hospital admission are at high risk of developing other adverse events. To this end, anticipated events that are consequences of the underlying disease, common events in the study population, or are part of the primary and secondary outcomes will be exempt from expedited reporting. Adverse events that are not listed as expected events (table 4) and are not deemed as serious and related to trial treatment (i.e. a SUSAR) by the assessing clinician are also exempt from reporting.

A SAE judged by the Investigator or medical monitor (in this case the CI), to have a reasonable causal relationship with the trial medication will be regarded as a Serious Adverse Reaction (SAR). The medical monitor will also assess all SARs for expectedness. If the event meets the definition of a SAR that is unexpected (i.e. is not defined in the Reference Safety Information (RSI) –see Section 10.1) it will be classified as a SUSAR.

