## 10.8. Reporting to the Competent Authority and Research Ethics Committee

## 10.8.1. Suspected Unexpected Serious Adverse Reactions

On becoming aware of a SUSAR, the Trial Manager (or delegate) will notify the Sponsor as soon as possible. The Sponsor will report a minimal data set of all individual events categorised as a fatal or life threatening SUSAR to the MHRA and Research Ethics Committee (REC) within 7 days. Detailed follow-up information will be provided within an additional 8 days. All other events categorised as SUSARs will be reported within 15 days.

SUSARs will be unblinded to allow reporting to REC and the MHRA.

Trial	TB-DILI Trial	Protocol	1.2	date:	02-Aug-2022	Page 41 of 58
name:		version:				

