# 14.2. Analysis of Outcome Measures

# 14.2.1. Planned Interim Analysis

No formal interim analyses are planned. However, an internal pilot has been built into the trial to allow a feasibility assessment which will examine recruitment and retention. This will be continually monitored, and a formal review will take place 18 months after the first participant has been randomised. Recruitment will be measured against the overall recruitment target at 18 months. To assess retention in the maximum number of participants at 18 months, retention is defined as the proportion of participants for whom the primary outcome is evaluable a) at 12 months for participants recruited within the first six months, b) at end of treatment for subsequent recruits.

	Black (stop the study)	Red (proceed with recovery plan)	Amber (proceed with changes)	Green (proceed)
% Threshold				
Trial recruitment	<50%	50 – 79%	80- 99%	> 100%
Recruitment rate (site/month)	<0.12	≥0.12 - ≤ 0.18	> 0.18 - <0.23	> 0.23
Retention (primary outcome obtained)	<50%	50-79%	80 – 99%	> 100%
Adherence*	<50%	50-74%	75-89%	> 90%

Table 6: Internal pilot progression criteria.

\*Adherence defined in section 7.5.2.

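### The outcome exemption in section 10.3 leaves severe or fatal DILI recurrence normally outside the only expedited route to the DMC chair, and the SAE sections disagree on what sites must report

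*Protocol*

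**What the plan says.** **Exemption.** Section 10.3 states that events that are "part of the primary and secondary outcomes will be exempt from expedited reporting". Section 2.2 makes DILI recurrence the primary outcome, and severity of recurrence and 12-month mortality secondary outcomes.

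**Expectedness.** Section 10.3 judges expectedness against the reference safety information and points to section 10.1, where Table 4 lists hepatitis, acute hepatic failure and liver injury as expected. Section 10.5 names the product summaries as the reference.

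**Routes to the DMC.** Section 10.2 sends confirmed SUSARs to the DMC chair in an expedited way. It has the DMC monitor endpoint events that are not expedited, through reports at a frequency the committee sets, at least annual. Section 10.10 has the DMC review all SAEs. Under section 16.5, "the DMC is scheduled to meet 6 months and 18 months after the recruitment of the first participant and annually thereafter" during recruitment. The same section adds "An emergency meeting may also be convened if a safety issue is identified" and "the DMC may, at their discretion, request to meet more frequently or continue to meet following completion of recruitment".

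**SAE reporting.** Section 10.4 limits SAE reporting to events the clinician judges related, glosses these as SUSARs, and sets a 24-hour limit for the form to reach NCTU. Its Sites paragraph requires a form for any SAE. Section 10.8.1 sends "all individual events categorised as a fatal or life threatening SUSAR to the MHRA and Research Ethics Committee (REC) within 7 days". Section 10.8.2 puts all SAEs and SARs in the annual report.

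**The concern.** Recurrent liver injury is the main hazard of restarting these drugs. The protocol's own background says that, among those with DILI on treatment, "16% develop jaundice and 5.3% acute liver failure; the latter is the most severe outcome of DILI, of which 22% can be fatal". Yet a severe recurrence is both exempt as an outcome and listed as expected, which makes the trial's central toxicity one of the events least likely to be escalated promptly. The emergency meeting depends on someone recognising a safety issue and telling the committee, and the protocol does not say which event should prompt that.

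The conflict over SAE forms is a separate problem. Sites that follow different paragraphs would send different events. The DMC would then see an incomplete SAE record that varies by site. Because sites know the allocation, that incompleteness could also differ between arms.

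**Working it through.** **1. The plan's own figure.** The expected counts below rest on section 14.1.1: 10% against 1.5% recurrence, two-sided 5%, pooled Z-test. This gives 156 per arm for 90% power. With 157 per arm, power is 90.3%. Allowing 10% loss, 156/0.9 = 173.3, so 174; the plan recruits 175. The sample size reproduces and is not in dispute.

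**2. Three events traced through the text.**

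| Provision | Serious category 3 recurrence, related, listed as expected | Death judged unrelated | Fatal SUSAR |
|---|---|---|---|
| 10.3, outcome exemption | Exempt | Exempt (mortality) | Exempt if read literally |
| 10.3, second paragraph | SAR, not SUSAR | Not a SAR | Classified as SUSAR |
| 10.4, read as related SAEs | Form to NCTU in 24 hours | No form | Form |
| 10.4, read as SUSARs | No form | No form | Form |
| 10.4, Sites | Form | Form | Form |
| 10.2, expedited to DMC chair | No | No | Yes |
| 10.8.1, MHRA and REC in 7 days | No | No | Yes |
| 10.8.2, annual report | Included | Included | Included |
| 10.10, DMC review | Included, no timing | Included, no timing | Included |

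Two results follow. First, in the first two columns no row gives the DMC chair a timed notice. Second, sections 10.8.2 and 10.10 need all SAEs, which the SAE forms cannot supply if section 10.4 is followed on either reading.

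The first column says listed as expected for a reason. The protocol's definition of an unexpected reaction covers severity and outcome as well as nature, so an individual severe or fatal case could still be classed as a SUSAR. That is a case-by-case judgement, not a dependable route.

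**3. Schedule.** With 48 months of recruitment, meetings fall at months 6, 18, 30 and 42. The gaps are 6, 12, 12 and 12 months. The last participant's follow-up ends at 48 + 12 = 60, which is 60 − 42 = 18 months after the last scheduled meeting. The at-least-annual reports in section 10.2 are not limited to recruitment.

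**4. Size.** Assumptions: even recruitment; 1:1 allocation; the 5.3% liver failure share and 22% fatality from section 1.1 apply to recurrences. The documents give no share for category 3, so liver failure stands in for it. Counts are treated as Poisson, with P(at least 1) = 1 − exp(−mean).

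- Accrual: 350/48 = 7.29 per month; 87.5 per 12 months, 43.75 per arm.
- Recurrences per 12-month gap at planned rates: 43.75 × (0.10 + 0.015) = 5.03.
- Liver failures per gap: 5.03 × 0.053 = 0.27; P = 23%.
- Whole trial: 175 × 0.115 = 20.1 recurrences; × 0.053 = 1.07 liver failures, P = 66%; × 0.22 = 0.23 fatal, P = 21%.
- With 25% in the control arm, the rate in the pyrazinamide arm of the 45-patient trial in section 1.1: 43.75 × 0.265 = 11.6 recurrences per gap; × 0.053 = 0.61 liver failures, P = 46%; fatal over the trial 175 × 0.265 × 0.053 × 0.22 = 0.54, P = 42%.
- Deaths from any cause, if the 5.3% mortality quoted in section 1.1 for drug-sensitive TB applied: 350 × 0.053 = 18.6 over the trial.

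**The case against.** The protocol is far from silent on safety. The exemption covers expedited reporting only. Section 10.2 provides for DMC monitoring of exactly these endpoint events, and already sends SUSARs to the chair. The DMC may meet sooner, in an emergency or after recruitment closes. The TSC meets about every six months after month 18 and "ultimately carries the responsibility for deciding whether the trial needs to be stopped on the grounds of safety or efficacy". A blinded panel judges every possible DILI episode, and section 9.1.4 discontinues the allocated regimen at recurrence. All of this stands, and it rules out several stronger readings.

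- A reader might infer that severe harm goes unseen for a year. The 12 months is the longest gap between scheduled DMC meetings during recruitment, not a limit on when the DMC can act.
- A reader might infer that no stopping guidance exists, because the only numeric stop criteria (Table 6) concern feasibility. Sections 16.4 and 16.5 cite TSC and DMC charters that are not shown and may hold it.
- A reader might fear for the type I error. Stopping at nominal p < 0.05 at any of four reviews, plus the final test, would give about 15%, but section 14.2.1 says "No formal interim analyses are planned" and nothing suggests that practice.
- A reader might infer that section 10.3 cancels the seven-day duty for fatal SUSARs. Its second paragraph keeps SUSAR classification in force, so this is loose wording rather than a cancelled duty.

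The inputs can also be challenged. The 25% rate comes from a very small trial, while the 175-patient trial in section 1.1 reported about 10%. The liver failure share describes DILI on treatment generally, not recurrence under monitored reintroduction. Only the control arm restarts pyrazinamide, and section 1.2.3 calls both regimens standard of care.

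None of this supplies a timed route for a severe, expected recurrence, or makes the SAE sections agree.

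**Conclusion.** The point holds in a limited form. As worded, section 10.3 exempts severe or fatal recurrence and death from expedited reporting. Because Table 4 lists the relevant liver events as expected, a severe recurrence would normally miss the only stated expedited route to the DMC chair. It would reach the committee through reports required at least annually and meetings up to 12 months apart during recruitment, unless someone calls an emergency meeting that the protocol ties to no defined event. Separately, sections 10.4, 10.8.2 and 10.10 cannot all be followed.

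The events concerned are few but plausible. The chance of at least one acute liver failure in a 12-month gap is 23% at the planned rates and 46% if control recurrence is 25%, on the accrual and severity assumptions above. The textual conflicts depend on none of these figures and on no unseen document. The finding is about notification and consistency; it does not show that the trial lacks safety oversight.

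**What to change.** 1. Reconcile sections 10.3, 10.4 (including its Sites paragraph), 10.8.1, 10.8.2 and 10.10 so that one rule says which SAEs sites send, to whom and by when.
2. In section 10.4, stop equating a related SAE with a SUSAR: a related SAE is a SAR, and only an unexpected one is a SUSAR.
3. In section 10.3, state that the outcome exemption does not remove SUSARs, deaths or Table 2 category 3 and 4 recurrences from prompt notification to NCTU and onward to the DMC chair. Agree the timing with the DMC.
4. In section 16.5, cite the DMC charter for any safety-monitoring guideline, for what prompts an emergency meeting, and for review after recruitment closes.

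No stopping threshold, event count or clinical rule is proposed; those belong to the DMC and its charter. The cost is an amendment to wording plus some extra expedited forms and listings. On the rough figures above, that is about 19 deaths and one or two liver failures (1.07 at the planned rates; 175 × 0.265 × 0.053 = 2.46 at the higher rate) over five years, plus any other category 3 recurrences. Sample size, final analysis and patient procedures are unchanged.

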# 16.6. Finance

This trial is funded by the National Institute for Health Research (NIHR) Health Technology Assessment (HTA) programme (funder reference: 12/95/15).

# **17.Ethical Considerations**

The trial will be conducted in accordance with the ethical principles that have their origin in the Declaration of Helsinki, 1996.

The trial will be conducted in accordance with the UK Policy Framework for Health and Social Care Research 2018, the applicable UK Statutory Instruments, which include the Medicines for Human Use (Clinical Trials) Regulations 2004 and subsequent amendments, the Data Protection Act 2018, The Human Tissue Act 2008 and Human Tissue (Scotland) Act 2006 (if applicable) and Guidelines for Good Clinical Practice (GCP). This trial will be carried out under a Clinical Trial Authorisation in accordance with the Medicines for Human Use (Clinical Trials) regulations. The protocol will be submitted to and approved by the MHRA and REC prior to circulation.

# **18.**Confidentiality and Data Protection

Personal data recorded on all documents will be regarded as strictly confidential and will be handled and stored in accordance with the Data Protection Act 2018.

Participants will always be identified using their initials and unique trial identification number on the eCRF and correspondence between the NCTU and the participating site.

Participants will give their explicit consent for a copy of their ICF to be shared with the NCTU. This will be accessible via the trial randomisation system and will be used by the NCTU to monitor the consent process.

The Investigator must maintain documents not for submission to the NCTU (e.g. Participant Identification Logs) in strict confidence. In the case of specific issues and/or queries from the regulatory authorities, it will be necessary to have access to the complete trial records, provided that participant confidentiality is protected.

The NCTU will maintain the confidentiality of all participants' data and will not disclose information by which participants may be identified to any third party other than those directly involved in the treatment of the participant and organisations for which the participant has given explicit consent for data transfer (e.g. competent authority, Sponsor). Representatives of the NCTU and Sponsor may be required to have access to a participant's notes for quality assurance purposes, but participants should be reassured that their confidentiality will be respected at all times.

# 19. Insurance and Indemnity

Nottingham University Hospitals NHS Trust will act as Sponsor for the trial. Delegated responsibilities will be assigned to the NHS Trusts taking part and NCTU.

Insurance and indemnity for trial participants and NHS trial staff are covered within the NHS Indemnity Arrangements for clinical negligence claims in the NHS, issued under cover of HSG (96) 48. There are no special compensation arrangements, but trial participants may have recourse to the NHS complaints procedure.

Trial	TB-DILI Trial	Protocol	1.2	date:	02-Aug-2022	Page 50 of 58
name:		version:				

The University of Nottingham has appropriate and typical insurance coverage in place (including, but not limited to Clinical Trials, Professional Indemnity, Employer's Liability and Public Liability policies) in relation to the Institution's Legal Liabilities arising from the University's activities and those of its staff, whilst conducting University business and research activity.

The Nottingham University Hospitals NHS Trust is independent of any pharmaceutical company, and as such it is not covered by the Association of the British Pharmaceutical Industry (ABPI) guidelines for participant compensation.

# 20. Publication Policy

The dissemination of the proposed research findings will be via a published NIHR HTA monograph, research papers for publication in peer reviewed journals, presentation at medical conferences and communication of our findings to groups involved in guideline development.

Results of this trial will be submitted for publication in a peer reviewed journal. The manuscript will be prepared by the Chief Investigator and Trial Management Group and authorship will be determined by mutual agreement.

Any secondary publications and presentations prepared by Investigators must be reviewed by the Chief Investigator and NCTU. Manuscripts must be submitted to either party in a timely fashion and in advance of being submitted for publication, to allow time for review and resolution of any outstanding issues. Authors must acknowledge that the trial was performed with the support of the Nottingham University Hospitals NHS Trust.

During the course of the trial, press releases may be issued from NCTU. Presentations or other material prepared by local investigators to publicise the trial must be reviewed by the Chief Investigator and NCTU. No party will be entitled to submit any publicity material without prior approval from NCTU.

Trial participants will be asked whether or not they would like to receive a summary of the research findings and invited to leave contact details by which they will be contacted with the research summary at the end of the project, following the publication of results.

ſ	Trial	TB-DILI Trial	Protocol	1.2	date:	02-Aug-2022	Page 51 of 58
	name:		version:				

